## Project Summary

Numerous (>40) epidemiologic reports have linked insomnia and nightmares to suicidal ideation and suicide death. We are presently engaged in a project which tests the hypothesis that treatment of insomnia in depressed patients with hypnotic medications will reduce the intensity of suicidal ideation. This ongoing project is called Reducing Suicidal Ideation Through Insomnia Treatment (REST-IT).

We have now acquired and analyzed new data since the inception of the present project that reveals that nightmares and disturbing dreams are more strongly related to the intensity of suicidal ideation than is insomnia itself. We therefore propose to target treatment of nightmares in suicidal patients experiencing nightmares as part of post-traumatic stress disorder (PTSD). This new effort is named Reducing Suicidal Ideation Through Treatment of Nightmares in PTSD (REST-ON-PTSD). REST-ON-PTSD will offer treatment with open label selective serotonin reuptake inhibitors (SSRIs) for PTSD, or open label treatment for bipolar disorder, combined with randomization to prazosin versus placebo. SSRIs are the only medications approved by the FDA for treatment of PTSD, while prazosin is the best-practice pharmacologic treatment for nightmares.{Aurora, 2010 1365 /id} REST-ON-PTSD is designed to be a small, randomized controlled clinical trial intended to generate pilot data to estimate effect sizes for prazosin treatment in reducing suicidal ideation in suicidal PTSD outpatients who have nightmares and disturbing dreams, with the following Specific Aims:

Primary Aim: We will estimate the effect size of prazosin on the intensity of suicidal ideation in PTSD outpatients with nightmares and disturbing dreams.

Hypothesis 1. Prazosin, combined with an SSRI or open label treatment for bipolar disorder, will reduce suicidal ideation in suicidal PTSD outpatients who have nightmares and disturbing dreams.

Secondary Aim: We will estimate the effect size of prazosin in reducing the intensity of nightmares and disturbing dreams in suicidal PTSD outpatients with nightmares and disturbing dreams.

Hypothesis 2. Prazosin, combined with a SSRI or open label treatment for bipolar disorder, will reduce the intensity of nightmares and disturbing dreams in suicidal PTSD outpatients with nightmares and disturbing dreams

Tertiary Aims: We will assess the safety of prazosin in the treatment of suicidal PTSD outpatients with nightmares and disturbing dreams. We will assess the impact of prazosin in salivary amylase, which is a test of systemic adrenergic tone.

Impact on the Field This application has the potential to change providers' practice in the approach to treating PTSD patients with mild-moderate suicidal ideation. Physicians have limited options in pharmacologic approaches to reduce suicide risk. The success of prazosin in reducing suicidal ideation in PTSD patients would be a novel strategy for a serious public health problem with few known solutions.

### 3. RESEARCH STRATEGY

#### 3.a. Significance

Suicide is a leading cause of death across all ages and occurs at a rate of 10-11 cases per 100,000 persons per year in the USA.{Mann, 2005 819 /id} It is the third-leading cause of death in the USA in those under 30 years of age.{Mann, 2005 819 /id} Across the world, the rank order of suicide in global mortality has risen between 1990 to 2010 from the 14th to 13th place in cause of death. An estimated 883,000 persons died by suicide around the world in 2010. {Lozano, 2012 1364 /id} Most suicides occur in the context of an active psychiatric disorder.{Mann, 2005 819 /id}

Suicide rates in the US military have drawn recent scrutiny as it has been revealed that more American service men died of suicide in 2012 than died of battle wounds in Afghanistan. Recent expert reports indicate that suicide death is indeed higher in US war-veterans as compared with non-military age-matched controls, that young men have the highest age-adjusted disproportionate risk, and that Iraq deployment indicates an especially high risk.{Krysinska, 2010 1373 /id;Rozanov, 2012 1376 /id} The standard mortality ratio (SMR) for the entire US Army was actually lower than expected until 2008, at which time the SMR exceeded 100, and in 2009 the SMR was estimated at 115.3 (95% CI 113.5-117.1).{Behavioral and Social Health Outcomes Program, 2012 1378 /id}

At least some of this elevated risk among returning war veterans is believed to be explained by post-traumatic stress disorder (PTSD), a mental disorder distinguished by reliving traumatic experiences, heightened physiologic arousal, and emotional numbing. Again, there is some debate as to whether PTSD is linked to excess suicide death, but there is a consensus that it is linked to elevated suicidal ideation and suicide attempts, and {Krysinska, 2010 1373 /id;Rozanov, 2012 1376 /id} during Vietnam PTSD represented a 4-fold increased risk for suicide.{Rozanov, 2012 1376 /id} Although >50% of persons with PTSD also meet criteria for MDD,{Post, 2011 1372 /id} and while the risk of suicide is further amplified by the presence of major depressive disorder (MDD), PTSD is still an independent risk factor for suicide.{Krysinska, 2010 1373 /id;Rozanov, 2012 1376 /id}

Risk factors for suicide include both unmodifiable and some potentially modifiable factors.{Maris, 2002 1011 /id;Coryell, 2005 674 /id;Brown, 2000 314 /id} Examples of unmodifiable factors are advancing age, male gender, and Caucasian ethnicity. Potentially modifiable risk factors include symptoms of depression, hopelessness, social isolation, active alcohol/substance use, and severe sleep disturbance. As a predictor, insomnia is stronger than a specific suicide plan in predicting near-lethal suicide attempts,{Hall, 1999 801 /id} yet sleep disorder is often overlooked in reviews of risk factors for suicide and suicide prevention.{Oquendo, 1997 1019 /id} The need to broaden the search for modifiable risk factors is epitomized by this recent statement: "nowhere is the lack of proven therapeutic methods greater than in the prevention of suicidal behavior."{Oquendo, 2003 1018 /id}

As we have reviewed elsewhere,{McCall W Vaughn, 2011 1253 /id;McCall, 2010 1193 /id;McCall WV, 2013 1475 /id} >60 research studies link insomnia to suicidal ideation, suicidal behavior, or suicide death, including >40 studies in adults. {Barraclough, 1975 926 /id;Agargun, 1997 805 /id;Agargun, 1997 8 /id;Agargun, 1998 804 /id;Smith, 2004 799 /id;Bernert, 2005 798 /id;Chellappa, 2007 892 /id;Bernert, 2009 1044 /id;Agargun, 2007 891 /id;Sjostrom, 2007 752 /id;Goodwin, 2008 1013 /id;Fawcett, 1990 76 /id;Tanskanen, 2001 797 /id;Fujino, 2005 809 /id;Turvey, 2002 397 /id;Li, 2010 1196 /id;Tishler, 1981 929 /id;Bailly, 2004 933 /id;Choquet, 1989 808 /id;Choquet, 1993 807 /id;Liu, 2004 928 /id;Vignau, 1997 806 /id;Roberts, 2001 803 /id;Cukrowicz, 2006 927 /id;Barbe, 2005 931 /id;Goldstein, 2008 930 /id;Nadorff, 2011 1197 /id;Bjerkeset, 2011 1246 /id;Brower, 2011 1247 /id;Krakow, 2011 1248 /id;Carli, 2011 1249 /id;Fitzgerald, 2011 1254 /id;Agargun, 2003 828 /id;McCall, 2010 1193 /id} Insomnia and nightmares were the most common sleep disturbances associated with suicide, even after adjusting for severity of depression. Five studies were prospective and showed that insomnia was a risk for suicide death. {Fawcett, 1990 76 /id;Tanskanen, 2001 797 /id;Fujino, 2005 809

/id; Turvey, 2002 397 /id; Bjerkeset, 2011 1246 /id} The clinical association of insomnia, nightmares, and suicidal ideation is paralleled by the physiologic finding that, among depressed outpatients, there is an inverse relationship between REM sleep latency and intensity of suicidal ideation.{Agargun, 2003 828 /id} A higher rate of depressed patients report unpleasant dreams (39%) as compared with persons who are not depressed (14%), even when both the depressed and nondepressed persons share similar life circumstances.{Cartwright, 1996 1371 /id} Whether the depressing dreams of depressed patients are conceptually the same as the nightmares of PTSD is unclear, although it is clear that bad dreams are a risk factor for suicidal ideation, independent of a PTSD diagnosis.{Nadorff, 2011 1197 /id}

Selective serotonin reuptake inhibitors (SSRIs) are a mainstay treatment for PTSD, and two of these, sertraline and paroxetine, are FDA approved for PTSD. However, SSRIs do not address all PTSD-symptoms equally well. For example, SSRIs are beneficial for symptoms like irritability, and but do less for sleep disturbance.{Baker, 2009 1375 /id} Abnormal, elevated activity within the brain's noradrenergic system is believed to play a role in the symptoms of hyper-arousal, such as nightmares, and SSRIs do not directly impact the noradrenergic system.{Krystal, 2009 1374 /id} In contrast, FDA-approved, foundational treatments for bipolar disorder include lithium, valproic acid, lamotrigine, quetiapine, asenapine, olanzapine, ziprasidone, lurasidone ,and the olanzapine-fluoxetine combination.

Given these facts, we propose that dampening the hyperarousal of PTSD with a blocker of noradrenergic receptors, would lead to less problematic nightmares, and culminate in lesser intensity of suicidality thinking.

[figure not shown]
The American Academy of Sleep Medicine states that the best-practice pharmacologic treatment for nightmares is prazosin.{Aurora, 2010 1365 /id} Prazosin is an  $\alpha_1$  adrenergic receptor blocker approved for use as an antihypertensive. The cardiovascular effects of the drug were fully characterized more than 30 years ago.{Colucci, 1982 1369 /id} The drug is slowly titrated starting with 1-mg capsules in order to minimize the risk of hypotension, with an average dose of 6-15 mg per day for antihypertensive effects. It generally has no effect on heart rate. The most common side effects at these doses are: dizziness 10.3%, headache 7.8%, drowsiness 7.6%, lack of energy 6.9%, weakness 6.5%, palpitations 5.3%, and nausea 4.9%.

A number of randomized controlled comparisons of prazosin have proven that prazosin is superior to placebo in reducing nightmares. These studies have been primarily in the study of PTSD-related nightmares, with some preliminary information suggesting that prazosin may also reduce non-nightmare awakenings in PTSD patients.{Thompson, 2008 1367 /id} The most recent large study of prazosin for PTSD-related nightmares in American soldiers found that a mean bedtime dose of  $15.6 \pm 6.0$  mg in men, and  $7.0 \pm 3.5$  mg in women, reached over a period of 5-6 weeks, was highly effective, with blood pressure changes, as compared with placebo. The most common side effects in this study were lightheadedness (25% versus 20% for placebo) and nasal congestion (22% versus 11% for placebo).{Raskind, 2013 1474 /id}

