### METHODS OF THE PRESENT PROPOSAL

#### 3.e.2. OVERVIEW

This pilot study will enroll 20 participants with PTSD who have prominent problem with nightmares and a mild-to-moderate degree of suicidality. Participants will have been on a stable dose of an SSRI or open label treatment for bipolar disorder, at a therapeutic dose, for at least one month before baseline assessment. Patients with bipolar disorder will have been on a stable dose of FDA-approved treatment for bipolar disorder

(lithium, valproic acid, lamotrigine, quetiapine, asenapine, olanzapine, ziprasidone, lurasidone or the olanzapine-fluoxetine combination). Patients who meet all qualifying requirements at baseline will then be randomized in a 1:1 proportion to either prazosin 1 mg at bedtime or placebo. Over the course of 6 weeks, the dose of prazosin will be increased as tolerated, while the dose of the SSRI or medication for bipolar disorder is held constant. Participants will be re-assessed weekly for 8 weeks post-randomization, and only enough prazosin will be provided to last until the next visit.

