### 3.e.4. Treatment

#### Dose finding during randomized care

Participants who pass all screening and baseline-week assessments immediately begin one capsule of prazosin 1 mg capsule or a placebo. Study drug will be taken at bedtime. Participants will be called by study-staff after two nights, and if participants do not appreciate an improvement in their disturbing dreams and nightmares after 2 nights, then they are allowed to increase their bedtime study drug to two capsules, following the design of Raskind et al (Table 1).{Raskind, 2013 1474 /id}

REST-ON participants return to the clinic each week for routine follow up and assessment of treatment response, BP, and adverse events. If the patient and research physician judge the benefit of study drug to be inadequate for sleep continuity or nightmares, then the dose may be increased according to the titration schedule below. At any point during the medication titration, upward dosages will not be permitted if: systolic BP <90, or diastolic <50, either sitting or standing, or if the patient has felt faint or near-syncopal, or has had a syncopal attack. The final research visit will be at the end of the eighth week of randomized treatment, and decisions will be finalized at that time of transition to care as usual.

Table1 Prazosin dose titration schedule

Week/Day	Men's Dose	Women's Dose
Days 1-2	1	1
Days 3-7	2	2
Week 2	4	2
Week 3	6	4
Week 4	10	6
Week 5	15	10
Week 6	20	10

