#### Randomization and blinding

Randomization of the 20 participants will be accomplished with blocked randomization: 5 blocks of two patients each. Blinding will be single blind, as the placebo we will use will be a generic lactose-filled capsule, and we will not attempt to create a matching placebo for the purposes of this pilot study. Our reasons for not making a matching placebo are as follows: (1) prazosin is generic and the physical appearance of the prazosin capsules may be subject to change, (2) the vast majority of participants will not know what generic prazosin looks like and hence will remain blind even if the placebo does not look like generic prazosin, (3) our most important outcome measures are self-report measures and hence not subject to investigator bias, (4) from prior experience, we have learned that creation of matching placebos would incur a minimum expense of about \$1000 - an expense that is unnecessary for our purposes.

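### Sex decides which prazosin schedule applies, yet allocation is not stratified by sex and the model has no sex term: modest, avoidable noise rather than bias

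*Combined protocol and SAP*

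**What the plan says.** - **Schedule.** Table 1 (section 3.e.4, Dose finding during randomized care) has one column for men and one for women. They agree up to day 7 and then separate: 4 against 2 in week 2, 6 against 4, 10 against 6, 15 against 10, and 20 against 10 in week 6. Moving up is conditional: if benefit is judged inadequate, "the dose may be increased according to the titration schedule below", subject to blood-pressure and syncope limits.
- **Source of the schedule.** Section 3.e.4 says that the dosing follows the cited trial in soldiers. Section 3.a reports that trial as reaching a "mean bedtime dose of $15.6 \pm 6.0$ mg in men, and $7.0 \pm 3.5$ mg in women".
- **Allocation.** Section 3.e.2 has patients "randomized in a 1:1 proportion to either prazosin 1 mg at bedtime or placebo". The method is given under Randomization and blinding: "Randomization of the 20 participants will be accomplished with blocked randomization: 5 blocks of two patients each". No stratification factor is named anywhere.
- **Analysis.** Section 3.f uses repeated-measures models, takes the treatment effect as change from baseline to the end of randomised treatment, and mentions adjustment for baseline measures. It names no sex term and no summary of dose by arm or sex. Its estimates are meant to feed the design of a larger trial.
- **Sex and risk.** On suicide, section 3.a states: "Examples of unmodifiable factors are advancing age, male gender, and Caucasian ethnicity".
- **Expected sex mix.** Section 6.i expects about half women. Table 3 shows 14 women and 6 men in its racial total, and 12 and 6 in its ethnic total.

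**The concern.** The Primary Aim is a single effect size for prazosin on suicidal ideation. The active treatment is in practice two schedules, and sex decides which one a participant can follow. With about 10 participants per arm and no stratification, chance settles how many men fall in the prazosin arm. That has two possible consequences. The schedule available to the active arm may lean towards one column of Table 1. And if sex is related to the outcome, a sex imbalance becomes part of the arm difference. Since the pilot exists to supply an effect size and variance to the next trial, avoidable noise of this kind is worth removing if removal is cheap.

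**Working it through.** **1. The plan's own allocation figure.** The block statement gives 5 × 2 = 10 patients, not 20. Ten blocks of two, or five blocks of four (two per arm in each), would give 20. The check below takes 20 patients, 10 per arm.

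**2. Chance split of men.** With M men among 20 and 10 allocated to prazosin, the number of men on prazosin, k, is hypergeometric: P(k) = C(M,k) × C(20−M, 10−k) / C(20,10), where C(20,10) = 184,756.

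*M = 6 (Table 3, racial total):*
- 3:3 split: 20 × 3,432 / 184,756 = 37.2%
- 4:2 either way: 2 × 15 × 3,003 / 184,756 = 48.8%
- 5:1 or 6:0 either way: 2 × (6 × 2,002 + 1,001) / 184,756 = 14.1%. Half of this, 7.0%, is the chance of at most one man on prazosin.

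*M = 10 (section 6.i):*
- 5:5 split: 252² / 184,756 = 34.4%
- 7:3 or worse: 2 × (120² + 45² + 10² + 1) / 184,756 = 17.9%

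Simulating blocks of two with random entry order gives 14.2% and 18.0%, so small blocks do not protect the sex balance.

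**3. Schedule open to the prazosin arm.** The mean top entry of Table 1 over the 10 prazosin participants is (20k + 10(10 − k))/10 = 10 + k. With the cited trial's mean doses in place of the top entries, it is 7.0 + 0.86k mg.

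| Men of 20 | Central 95% range of k | Mean top entry (balanced) | At cited mean doses, mg (balanced) |
|---|---|---|---|
| 6 | 1 to 5 | 11 to 15 (13) | 7.9 to 11.3 (9.6) |
| 10 | 3 to 7 | 13 to 17 (15) | 9.6 to 13.0 (11.3) |

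The top-entry column averages ceilings. It does not describe doses taken.

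**4. Noise in the effect size.** Let g be the difference between the sexes in the analysed outcome, in SD units. The documents give no value, so g = 0.2 to 0.8 is an assumption. The arms' shares of men differ by (2k − M)/10, so imbalance shifts the arm difference by g(2k − M)/10. Its mean is zero and its SD is 2g × SD(k)/10.

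- SD(k) = √(10 × 0.3 × 0.7 × 10/19) = 1.05 for M = 6, and √(10 × 0.5 × 0.5 × 10/19) = 1.15 for M = 10.
- SD of the shift: 0.04, 0.11 and 0.17 for M = 6 at g = 0.2, 0.5 and 0.8; 0.05, 0.11 and 0.18 for M = 10.
- Sampling SE of a standardised difference with 10 per arm: about √(2/10) = 0.45.
- Combined at g = 0.5 and M = 10: √(0.447² + 0.115²) = 0.462, about 3% more than 0.447. At g = 0.8: √(0.447² + 0.184²) = 0.483, about 8% more.
- One particular 5:1 split (M = 6) or 7:3 split (M = 10) shifts the difference by 0.4g, which is 0.08 to 0.32 SD over the assumed range.

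**5. With two lists.** In blocks of two within each list, 6 men split 3:3 and 10 men split 5:5. An odd count leaves a difference of one. The mean top entry is then 13 or 15, with no spread from allocation. The gap between 13 and 15 remains, because it comes from who is recruited.

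**The case against.** The strongest case against is that an unstratified 20-person estimation pilot is an acceptable design. Four parts of that case stand.

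- A reader might infer from section 3.a that men differ in the primary outcome, so that imbalance biases the result. The documents do not support this. The sentence on male gender concerns suicide, not SSI-rated ideation, and it lists age and ethnicity beside it. Nothing says that sex predicts SSI level or change. Section 3.f works with change from baseline and mentions baseline adjustment, which would take up much of any sex difference already present at entry.
- A reader might infer that sex fixes the dose received. Table 1 sets a ceiling within titration by response and tolerability. The documents also report no difference in effect between the sexes, so different milligram doses do not by themselves make a pooled estimate misleading.
- A reader might infer that stratifying would settle the dose mix behind the effect size. It would not. That mix also depends on recruitment, where section 6.i and Table 3 disagree, and on titration.
- The noise is small beside sampling error, and with 6 men, 86% of allocations are 3:3 or 4:2.

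What the objection does not remove is that Table 1 makes sex a determinant of the available regimen, that the cited trial's mean doses differed by 15.6/7.0 = 2.2-fold under titration, and that the imbalance can be avoided at almost no cost. A practical objection is also fair: the gender form in section 3.e.3 includes transgender, not-sure and declined answers, and the protocol does not say how these map to Table 1.

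**Conclusion.** The point holds as a low-to-moderate priority improvement. Sex determines which schedule applies, neither allocation nor analysis takes account of it, and a marked imbalance is fairly likely: 14% for 5:1 or worse with 6 men, 18% for 7:3 or worse with 10. Over repeated randomisations there is no expected bias. The added noise has an SD of about 0.04 to 0.18 against a sampling SE of about 0.45. These figures assume 20 participants allocated 10 per arm, no dropout, a sex mix as in Table 3 or section 6.i, and a sex effect of 0.2 to 0.8 SD remaining in the analysed outcome, which is an assumption with no support in the documents. The schedule argument needs only Table 1 and does not depend on that sex effect. No view is taken on the doses.

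**What to change.** - **Section 3.e.4, Randomization and blinding:** allocate 1:1 from two lists, one per column of Table 1. In the same edit, reconcile the number and size of blocks with the 20 planned participants, and state which list applies to participants who do not report male or female.
- **Section 3.f:** include the stratification factor as a covariate alongside baseline in the repeated-measures models, and report the dose reached by arm and sex next to the effect size, together with the sex mix by arm. Readers planning the next trial can then see which mix of schedules the estimate reflects.
- **Section 6.i and Table 3:** bring the expected sex mix into agreement, since this sets the length of each list.

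The cost is one extra list, one degree of freedom and one descriptive table. With blocks of two, an unfinished block leaves a difference of at most one participant per sex. With blocks of four it could leave two, which is a reason to settle the block size first.

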### 3.b. The theoretical model

One of the favored models for the etiology of insomnia posits that hyperarousal leads to sleep loss. In other words, it is not the sleep machinery that is broken in insomnia, but rather an awake system that is in overdrive and is inhibiting the expression of sleep, via an overactive sympathetic nervous system.{Bonnet, 2010 1366 /id} The hyperarousal model of primary insomnia resonates with hypervigilence and hyperstartle reactions as core symptoms of PTSD, and is congruent with the finding that these sympathetic-autonomic symptoms are relieved by prazosin, an  $\alpha_1$  adrenergic receptor blocker. Sympathetic-autonomic hyperarousal may be a common pathway for insomnia, nightmares, and suicide risk. Therefore, our theoretical model (Figure 1, below) is that treatment of nightmares and disturbing dreams with an  $\alpha_1$  adrenergic receptor blocker leads to reduced intensity of suicidal ideation.

Figure 1

